#### **Brief Visual Memory Test – Revised (BVMT-R; Benedict, 1997)**

Like any of its word list learning analogs (e.g., the HVLT-R), this test involves multiple trial learning followed by delayed recall and recognition trials. However, the stimuli are abstract line drawings rather than words. The patient is shown a set of 6 abstract line drawings (in a 2x3 array) for 10 seconds and is then asked to draw

them in their correct location. This procedure is repeated for a total of 3 learning trials. After 25 minutes, delayed recall and recognition (identifying which 6 of 12 drawings were seen) trials are administered. The brevity of the task and the availability of 6 alternate forms make the test useful for repeated administrations. It is normed for persons aged 18-79 years. Reliability coefficients exceed .90, and test-retest reliability ranges from .60 to .84. Excluding the delay, which is filled with verbal tests, the BVMT-R can be completed in 15 minutes.

### **Self and Informant Rating of Executive Functions**

#### **Behavior Rating Inventory of Executive Function – Adult Version (BRIEF-A; Roth et al. 2005)**

The self-and informant-report forms consist of 75 items asking the person to report the frequency (never, sometimes, or often) with which certain behaviors have occurred during the month prior to evaluation. The behaviors measured relate to a variety of executive functions (e.g., self-monitoring, emotional control, behavioral inhibition and shifting, planning and organization) and are expressed in 2 indices (Behavioral Regulation Index and Metacognition Index) and an overall summary score (Global Executive Composite). There are also 3 response validity scales. Normative data are available for 1,050 persons for self-report and 1,200 informant reports. The test can be used with adults aged 18-90 years. Test-retest reliability for self-report clinical scores ranged from .82 to .93 over an average re-test interval of about 4 weeks, while informant report test-retest reliability ranged from .91 to .94. Test-retest values were still higher for the summary indexes. Patients and informants usually complete these forms in about 15 minutes.

#### **Testing order:**

The above tests should be performed in the following order:

1. HVLT-R immediate recall (3 trials);
2. Ruff 2 & 7;
3. Stroop;
4. Fill rest of 20-25 minute delay with starting the BRIEF;
5. HVLT-R Delayed recall and recognition;
6. BVMT-R Immediate recall (3 trials);
7. DKEFS verbal fluency tests;
8. Letter-Number Sequencing;
9. Continue the BRIEF as needed to fill the BVMT-R delay;
10. BVMT-R Delay recall and recognition;
11. Finish BRIEF.

### 7.3 DBS System Implantation

The DBS system implant visit should be performed no less than 2 weeks and no more than 1 month after the baseline #3 visit.

Implantation of the DBS system will be performed according to standard surgical procedure for Brodmann Area 25WM (Cg25) DBS implantation.

Pre-Operative Imaging: High resolution, 3D T1 weighted images will be obtained. On or before the day of surgery patients will have a stereotactic frame or appropriate bone fiducials applied using local anesthesia. Additional CT imaging for fusion is optional, as is the use of IV contrast.

Pre-Operative Planning: Standard software (e.g. Framelink, Brainlab, or other) is used to reconstruct the images in axial, coronal, and sagittal views, relative to the AC-PC plane.

The sagittal images will be used first. Surgeon will select an image several millimeters (mm) off midline clearly showing the white and gray matter of the cingulate gyrus. A tentative target point is selected at the center of the subgenual cingulate (Brodmann Area 25WM).

Next, the surgeon will convert to the coronal images perpendicular to the AC-PC plane. The midpoint of the subgenual cingulate gyrus is typically found in the coronal image containing the anterior-most section of the caudate nucleus. Thus the A-P position of the target can be confirmed by scanning a few images anterior and posterior to confirm proximity to this section.

Precise targets can then be selected bilaterally in this same coronal section. A point is selected on each side at the border of the white and grey matter, midway between the superior and inferior banks of the cingulate gyrus. The intended site is approximately 5-7 mm from the midline and 10 mm below the corpus callosum. After targets have been selected, the appropriate frame coordinates can be calculated and used for the stereotactic procedure.

Entry points can also be selected on the stereotactic planner if desired. This practice is variable at different centers. If entry planning is performed it is recommended that an entry site that is slightly anterior to the more typical burr hole used for STN-DBS. This is necessitated by the more anterior nature of this target. Anterior entry (~2cm anterior to the coronal suture) will avoid a difficult approach angle.

DBS Implantation: After sterile preparation of the operative field, burr holes are placed under local or general anesthesia. Again the slightly more anterior entry is recommended. A lateral position of 2-3cm from midline is also recommended. Dura and pia are opened under direct visualization. The

remainder of the operation is performed using an appropriate stereotactic frame or frameless guidance system.

One or more cannulas are inserted to the target coordinate. Microelectrode recording may be performed, at this point, to confirm the location of the grey-white junction within the target area. This procedure is optional.

A DBS electrode will be inserted into the target under fluoroscopic visualization. Once the electrode has been placed in the calculated target intra-operative diagnostic testing will be performed; however, no active deep brain stimulation will be delivered to the patient in order to protect the study blinding process. After confirmation of position the end of the lead is protected and excess lead is coiled in a sterile subgaleal pocket made by blunt dissection. The procedure is then repeated for the contralateral side.

Intraoperative Device Diagnostic Testing: The implanted leads will be tested for proper connectivity as well as impedance; however, no active stimulation will be delivered, so as to not break the blinding of the study.

IPG Implantation: The second stage of the operative procedure involves the implantation of lead extensions and the IPG. This will be performed immediately following the above procedure. The patient is given a general anesthetic and a sterile preparation is performed. The lead ends are accessed either by reopening the scalp incision or by making a smaller incision over the subgaleal pocket. The lead extension is then tunneled subcutaneously to a second incision just below the clavicle (can be left or right depending on patient preference). The extension wire is attached to the DBS leads proximally and to the battery distally. The implantable pulse generator is placed in a subcutaneous pocket that is made below the clavicle. Excess wire is coiled behind the IPG. Once again, a device diagnostic test will occur but no active stimulation will be delivered to the patient at this time.

Lead Localization: The lead will be imaged post-implantation to confirm lead location according to current neurosurgical procedures and/or CT scans. These images must be given to the Sponsor for future analysis.

#### **7.4 Concomitant Treatments**

All patients will have the ability to maintain their depression medication regimen as well as regularly scheduled psychotherapy to ensure study and therapy controls are maintained. For the 1-year study, all psychiatric care/decisions must be transferred to the study psychiatrist. For the first 6 months of the study, patients will not be able to add new medications (excluding sleep aids and other meds to manage non-depression related conditions) nor increase current antidepressant medication doses.

**Medication additions:**

For temporary insomnia, zaleplon, zolpidem, zopiclone, or chloral hydrate (a single dose nightly) or trazodone (< 100 mg) may be used, for a maximum of 14 nights during the study. Lorazepam (< 2 mg/d) may also be administered for treatment emergent anxiety for up to 14 days.

**Rescue medications:**

The study psychiatrist should first identify a need for a rescue based on his/her clinical judgment of worsening depression. In the event that a patient needs to be “rescued” due to a severe worsening of their depression (defined as patients who score 25% worse than their baseline average on the MADRS or worsening of suicidal ideation), prior to the completion of 6 months in the study, appropriate intervention may be initiated at the principal investigator’s discretion considering the protocol-specified guidance. The following guidance should be adhered to when the rescue protocol is initiated:

If a patient is rescued based on a 25% worsening of their MADRS score compared to the average MADRS Scores:

- The patient will be considered a treatment failure.
- The visit will serve as the patient’s endpoint data and the patient will be exited from the study. All end-of-study procedures should be performed.
- At the principal investigator discretion, medications may be added or changed as deemed in the best medical interest of the patient.
- Patients who were in either the control group or received active stimulation should enter a separate open-label protocol for long-term follow-up.

If a patient is rescued based on a worsening of suicidal ideation

- A patient who shows imminent suicidal intent but does not attempt suicide will be treated for the acute exacerbation of their symptoms. If the event can be treated with an acute intervention (less than 7 days) then the patient should resume participation in the trial and not be unblinded as to treatment.
- After the acute intervention, the patient must have a MADRS item 10 score of less than 5 to resume participation in the trial.
- After the acute intervention, the patient must resume their previous medication regimen if medications were changed.
- Patient’s medications must be stable for a minimum of 7 days prior to an effectiveness visit
- If the patient attempts suicide, or requires a long-term medication change he/she will be considered and followed as a treatment failure.

Patients who were in either the control group or received active stimulation should enter a separate open-label protocol for long-term follow-up.

At any time during the study the patient feels suicidal or in any danger from worsening depressive symptoms, they, or their caretaker should call their study psychiatrist immediately.

## 7.5 Postoperative Visits

[REDACTED]

[REDACTED]

### 7.5.1 Study Visits:

[REDACTED]

[REDACTED]

[figure not shown]
The image consists of a series of horizontal bars. The top half features a large black rectangular area with a single white rectangular cutout in the center. Below this is a white gap, followed by a series of black bars of varying widths. The bottom half is mostly black, with a few white bars of different widths. The overall effect is like a high-contrast, abstract representation of a signal or a series of steps.

[REDACTED]  
Patient evaluation will take place 52 weeks after the system is implanted. This visit will include the following:

#### **7.5.2 Control Group (Non-Active Stimulation):**

At the end of the 6 month visit, patients will be given the option to have device programmed and activated for DBS. Patient will then be followed monthly, until the end of the 52 week study.

#### **7.6 Long-Term Follow-Up**

All patients will be encouraged to enroll in a long-term follow-up study under a separate protocol sponsored by ANS to monitor the continued efficacy and safety of this system. Efficacy assessments and device related adverse events will be collected on all willing participants at specific intervals after they exit the currently proposed study. A separate study protocol and patient informed consent will be signed for this long term follow up study.

All study patients may have access to the device at no cost for battery replacement and or revision(s) until the device is commercially available in the United States. The patients/physicians must make a request to the study sponsor to have the device shipped to the appropriate location.

## **8 Adverse Events (AEs)**

### **8.1 AE Definitions**

An ADVERSE EVENT is “Any change, undesired, noxious or pathological in a patient or subject illustrated by signs, symptoms and /or laboratory changes that occur during a clinical trial, whether or not considered drug/treatment related.”

A SERIOUS/SEVERE AE is where the event is/causes:

- Life threatening or fatal
- Requires or prolongs hospitalization
- The patient to be disabled

A DEVICE RELATED AE is an anticipated (those events listed in section 8.4) or unanticipated (those events that occur that are not listed in section 8.4) event that occurs that is considered device related. A device-related event is one that the Investigator feels that the device (i.e. IPG, extension or lead) contributed in any way to the adverse event occurring. A stimulation-related event is one that resolves when stimulation is turned off or turned down.

A NON SERIOUS AE is an event other than one described above.

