## 2 Objective

### 2.1 Primary Objectives

To demonstrate the safety and efficacy of deep brain stimulation (DBS) to the subgenual white matter (Brodmann Area 25WM) as an adjunctive treatment for Major Depressive Disorder (MDD), single or recurrent episode.

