### **8.2 AE Recording**

All Adverse Events volunteered by the Subjects/Patients or elicited by the Investigator must be recorded on the AE forms provided. All serious/severe AEs must be recorded whether or not considered device/treatment related. All device related complications that occur during the study duration and/or malfunctions of study device should be recorded on the AE forms provided. Device complications are defined as those complications relating directly to the functioning of the stimulation system (i.e. IPG, extension or lead).

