#### **8.4 Anticipated Adverse Events and Complications**

Implantation of a deep brain stimulation lead is a surgical procedure that may expose the patient to the risks of post-operative pain, stress, or discomfort, intracranial hemorrhage, subcutaneous hemorrhage, intracranial infarctions, venous air embolism (air entering the veins), venous infarctions, symptomatic pneumocephalus (intracranial air causing confusion requiring an extra day stay in the hospital), seizure or convulsions, seroma, infection, aphasia, paralysis, stroke, death, cerebrospinal fluid leakage or abnormality. An additional neurosurgical procedure may be necessary to manage one of the above complications or to replace a fractured lead or to replace the pulse generator

The anticipated adverse events associated with the use of this device may include the following:

- Neuropathy;
- Neuralgia;
- Headache;
- Asthenia, hemiplegia or hemiparesis;
- Cognitive impairment, including confusion, abnormal thinking, hallucinations, alteration of mentation, amnesia, delusions, or dementia;
- Infection;
- Fever;
- Disequilibrium;
- Ataxia;
- Myoclonus;
- Hearing and visual disturbance;
- Paresis;
- Dystonia;
- Attention deficit;
- Dysarthria;
- Sleep disturbance;
- Suicide or Suicide attempt;
- Increase in drug side effects;
- Autonomic instability (change in vital signs);
- Urinary incontinence;
- Worsening depression symptoms (will not be considered an AE);
- Anxiety;
- Ruminativeness;
- Hypomania;

- Mania;
- Panic attacks;
- Obsessive compulsive disorder (OCD) symptoms;
- Psychosis;
- Seizure;
- Apathy;
- Eye disorder;
- Sweating;
- Diarrhea;
- Sensory deficit;
- Drowsiness;
- Difficulty breathing;
- Increased salivation;
- Nausea and/or vomiting;
- Rapid heart rate;
- Pneumonia;
- Skin disorder;
- Edema including periorbital;
- Syncope;
- Persistent pain or redness at the IPG site or the surgery site/extension;
- Pulling sensation along extension site;
- Allergic or rejection response to implanted materials;
- General erosion or local skin erosion over the pulse generator (IPG), burr hole cap, and/or extension;
- Undesirable changes in stimulation possibly related to cellular changes in tissue around the electrodes, changes in the electrode position, or loose electrical connections and/or lead fracture;
- Initial jolt or tingling during stimulation;
- Paresthesia;

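### Section 8.1 labels an event stimulation-related only if it resolves when stimulation is turned off or down, so fatal and irreversible events can never carry that label

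*Combined protocol and SAP*

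**What the plan says.** All references are to the combined protocol and SAP.

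- **Section 8.1, device-related events.** An event is device-related if the investigator feels that "the device (i.e. IPG, extension or lead) contributed in any way to the adverse event occurring". The test is one of judgement, and resolution plays no part in it.
- **Section 8.1, stimulation-related events.** The next sentence of the same paragraph reads: "A stimulation-related event is one that resolves when stimulation is turned off or turned down". This is the whole definition.
- **Section 8.1, serious events.** The first listed criterion is "Life threatening or fatal". Disability is another.
- **Section 8.2.** "All serious/severe AEs must be recorded whether or not considered device/treatment related".
- **Section 8.4.** The events anticipated with use of the device include "Suicide or Suicide attempt" and "Cognitive impairment, including confusion, abnormal thinking, hallucinations, alteration of mentation, amnesia, delusions, or dementia". Seizure, syncope, mania, hemiplegia and a first jolt or tingling while stimulated are also listed.
- **Section 8.5.** The investigator classifies each event. The rest of that section is a figure that is not shown.
- **Section 2.1.** Safety and efficacy together form the primary objective.

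**The concern.** The stimulation-related definition turns one piece of causal evidence, improvement when the exposure is reduced, into the only criterion. Such improvement supports causation where it can be observed. Its absence says little when the event could not have reversed, was already over, or occurred in a patient whose settings were never reduced. The label therefore measures reversibility rather than cause.

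This matters because of the design. Both arms are implanted, and for the first 6 months only stimulation separates them (section 3.1). A stimulation-related category is the natural place to distinguish harm from the experimental exposure from harm due to surgery or hardware. A category that shuts out deaths and permanent deficits cannot do that for the events that weigh most in a risk-benefit judgement.

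**Working it through.** No rate, power or sample-size calculation enters this point, and the plan states no figure to reproduce. The check is to apply the section 8.1 wording to kinds of event that the protocol itself names, and then to look for another rule that would change the answer.

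**Step 1. Apply the definition.** In each of the first four rows, suppose that stimulation truly caused the event.

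| Event | Can it resolve on turning stimulation off or down? | Stimulation-related under 8.1? | Device-related under 8.1? |
|---|---|---|---|
| Death, including completed suicide | No | Never | Yes, if so judged |
| Permanent deficit, such as lasting cognitive impairment | No | Never | Yes, if so judged |
| Seizure, syncope or brief jolt that is over before settings change | No, it has already ended | No | Yes, if so judged |
| Event still in progress at switch-off, which then stops | Yes | Yes | Yes, if so judged |
| Unrelated event that happens to fade after a reduction | It appears to | Yes, wrongly | Only if so judged |

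The first two rows follow by logic alone and need no assumption about frequency. The third holds only when the event ended before, or independently of, the change in settings; the fourth row shows the exception. The last row is a realistic case: under section 10 the device is switched off whenever a patient leaves the study, so an unrelated event that is ongoing at exit and later clears would meet the wording.

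**Step 2. Look for a second rule.** Sections 8.1 to 8.5, the visible parts of 9.7 and 9.8, and section 13 contain no other criterion for attributing an event to stimulation: no judgement, no timing rule, no plausibility test and no exception for events that cannot resolve. In the visible text the term itself occurs only in section 8.1.

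**Step 3. See where the excluded events go.** Serious events are recorded whatever their attribution (section 8.2). A fatal or permanent event can be called device-related if the investigator thinks that the device "contributed in any way to the adverse event occurring". It then sits in one group with hardware and implant problems, with nothing to mark it as due to stimulation.

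**Step 4. Direction of the error.** For fatal and irreversible harm the error runs one way: such events can only be left out. For reversible events it can run either way, because true cases may be missed and coincidental recoveries may be included. The net error in a total count of stimulation-related events is therefore not determined by the documents. The loss of its fatal and lasting part is.

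**The case against.** The strongest reply is that little depends on this label.

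- **Device-related attribution remains open.** The sentence stands inside the device-related paragraph and can be read as describing a subtype. The hardware named there is what delivers stimulation: section 4.1 says that the generator produces the pulses and that the lead carries the electrodes. Section 8.4 names many of the events at issue as associated with the device. This stands. A reader might infer that a suicide or a lasting cognitive change could not be attributed to the treatment at all; the documents do not support that. What is lost is the narrower label.
- **No event is lost.** All serious events are recorded (section 8.2), the safety variable in section 2.4 is the incidence of all adverse events, and the suicide-suspension and hemorrhage-termination criteria in section 13 do not use the label. This stands too. Saying that fatal events go uncounted would be true of the label only.
- **Randomization gives a comparison that needs no attribution.** Controls are unstimulated for 6 months, so all adverse events can be compared by arm. This holds for that period. After it, controls may have the device activated (section 7.5.2), and attribution then carries more of the weight.
- **No visible analysis uses the label.** Correct. Section 9.7 is redacted and part of 8.5 is not shown. A reader might infer that the trial's safety results will make stimulation look safer than it is; that would require the label to drive a reported result, which cannot be checked. For the same reason a table of all events by arm cannot be called missing.

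The reply limits the consequence but leaves the definition as it is. Section 8.1 states a rule, and the rule misclassifies.

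**Conclusion.** The point holds for the stimulation-related label. As written, no fatal or irreversible event can receive it, whatever the true number caused by stimulation. Events that end before, or independently of, a change in settings also miss it, and coincidental recoveries gain it. Any count built on the label would understate serious stimulation harm. The weakness matters most after month 6, when an unstimulated comparison group is no longer assured.

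The exclusion is total for fatal and irreversible events, and this rests on the wording alone. For everything else no size can be given: the documents provide no event rates, and an illustration with assumed rates would only return its inputs.

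Two further inferences should be resisted. One is that single-occurrence events can never qualify; one that is still in progress and stops at switch-off does. The other is that the primary safety conclusion is biased; with section 9.7 redacted, the documents neither show this nor rule it out. This is a definition that should be corrected in a trial with safety in its primary objective, not a demonstrated error in the safety analysis.

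**What to change.** Replace the sentence in section 8.1 with: *a stimulation-related event is one the investigator judges at least possibly caused by stimulation, whether or not it resolves when stimulation is reduced.* Treat the response to any reduction as supporting information only, not as a requirement. This brings the label into line with the judgement-based test that the same paragraph already uses for device-related events.

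The cost is one sentence, and the reported stimulation-related rate may come out slightly higher. The change concerns classification only and leaves programming and patient management untouched.
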